- In absence of liver metastases, alanine aminotransferase (ALT) and aspartate aminotransferase (AST) $< 3 \times$ ULN. If the participant has liver metastases, ALT and AST $\leq 5 \times$ ULN (elevated ALT or AST values must be stable for 2 weeks, without evidence of biliary obstruction by imaging)
- Fasting Serum amylase $\leq 2 \times$ ULN
- Fasting Serum lipase \leq ULN
- FPG ≤ 140 mg/dL (7.7 mmol/L) and Glycosylated Hemoglobin (HbA1c) $\leq 6.4\%$ (both criteria have to be met)

9. Participant is a man or a pre- or post-menopausal woman

Post-menopausal status is defined either by:

- Prior bilateral oophorectomy or
- Age ≥ 60 or
- Age < 60 and amenorrhea for 12 or more months (in the absence of chemotherapy, tamoxifen, toremifene, or ovarian suppression) and follicle-stimulating hormone (FSH) and/or estradiol in the post-menopausal range per local normal range. If patient is taking tamoxifen or toremifene and age < 60 , then FSH and plasma estradiol levels should be in post-menopausal range per local normal range.

Note: For women using therapy-induced amenorrhea other than ovarian radiation or goserelin, serial measurements (per local guidelines) of FSH and/or estradiol are needed to ensure menopausal status.

Pre-menopausal status is defined as either:

- Patient had last menstrual period within the last 12 months
OR
- If on tamoxifen or toremifene during the past 14 days, plasma estradiol and FSH must be in the premenopausal range per local normal range,
OR
- In case of therapy-induced amenorrhea, plasma estradiol and/or FSH must be in the premenopausal range per local normal range

10. Participant is willing to operate a smartphone including the telemedicine application and a medical device (glucometer)

11. Participant is willing to follow the requirements for remote participation.

12. Participant has signed ICF before any trial related activities and according to local guidelines.

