Grade 4 (FG > 500 mg/dL) [≥ 27.8 mmol/L]	
 Omit alpelisib confirm fasting status of the assessment. If non-fasting, re-check within 24 hours. 
Regardless of fasting status, consider IV fluids.
 
 Exclude confounding factors like e.g. urinary tract infection. Consult with diabetologist, initiate or intensify medication with appropriate anti-diabetic treatment (see Grade 3), re-check within 24 hours. If grade improves then follow specific grade recommendations If FG is confirmed as > 500 mg/dL and confounding factors could be excluded, permanently discontinue participant from alpelisib.
CTCAE v 4.03 is modified to allow fasting blood glucose values in addition to fasting plasma glucose values. * For specific recommendations please see Section 6.5.1.3 "Guidelines for the treatment of alpelisib induced hyperglycemia"	
Investigations (Hepatic) . Note: this is for newly occurred or worsened from baseline	
Isolated total Bilirubin elevation	

Dose Modifications for alpelisib as specified below. Combination drug may be continued while alpelisib dose is being held, at the investigators discretion, and as specified.	
Worst toxicity - CTCAE Grade (value)	Dose Modifications for alpelisib
Grade 1 (> ULN - 1.5 × ULN)	
 No dose adjustment is required. Initiate appropriate medical therapy and monitor as clinically indicated.
Grade 2 (> 1.5 to 3.0 × ULN)	
 Interrupt dose until recovery to Grade ≤ 1 and resume at the same dose if resolved in ≤ 14 days or resume at the next lower dose level if resolved in > 14 days.
Grade 3 (> 3.0 to 10.0 × ULN)	
 Interrupt dose until recovery to Grade ≤ 1, then resume at the next lower dose level.
Grade 4 (> 10.0 × ULN)	
 Permanently discontinue.
Isolated AST or ALT elevation	
Grade 1 (> ULN - 3.0 × ULN)	
 No dose adjustment is required. Initiate appropriate medical therapy and monitor as clinically indicated.
Grade 2 (> 3.0 to 5.0 × ULN)	
 Interrupt dose until recovery to Grade ≤ 1, then decrease dose level.
Grade 3 (> 5.0 to 20.0 × ULN)	
 Permanently discontinue.

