* "Active" skin toxicities: If there are no new lesions or new areas of involvement developing, and if lesion appearance is changing color from red to pale or light brown, it is likely the skin toxicity has begun to fade and is not to be considered "active" any longer. Treatment reduction can be considered for these areas. The appearance of skin toxicity may fade slowly, over 10 days or more but not requiring ongoing therapy.	
Immune system disorders	
Hypersensitivity	
Please see specific instructions in Section 6.5.1.6 "Guidelines for hypersensitivity"	
Investigations (Pulmonary disorders)	
Pneumonitis	
Please see specific instructions in Section 6.5.1.1 "Management of Pneumonitis/Interstitial lung disease"	
Investigations (Metabolic)	

Dose Modifications for alpelisib as specified below. Combination drug may be continued while alpelisib dose is being held, at the investigators discretion, and as specified.	
Worst toxicity - CTCAE Grade (value)	Dose Modifications for alpelisib
Asymptomatic amylase and/or lipase elevation (see also Section 6.5.1.4 "Follow-up on amylase or lipase elevation (≥ CTCAE Grade 3")	
Grade 1 (> ULN - 1.5 × ULN)	
 Maintain dose level.
Grade 2 (> 1.5 to 2.0 × ULN)	
 Maintain dose level.
Grade ≥ 3 (> 2.0 × ULN)	
 Omit dose until resolved to baseline, then 
 If resolved in ≤ 14 days, maintain dose level. If resolved in > 14 days, then decrease dose level. Note: In cases of isolated amylase elevations only, dosing may be maintained provided amylase fractionation demonstrates that pancreatic amylase is ≤ Grade 1. Monitor total amylase (and continue to assess fractionated amylase) as specified in Section 6.5.1.4 "Follow-up on amylase or lipase elevation (≥ CTCAE Grade 3"
Note: Withhold trial treatment for acute onset of new or progressive unexplained abdominal symptoms, such as severe pain or vomiting; and perform diagnostic procedures (e.g., abdominal CT scan or ultrasound) to exclude pancreatic pathology.	
Investigations (any other)	
Other adverse events	
Grade 1 or 2	
 Maintain dose level.
Grade 3	
 Omit dose until resolved to ≤ Grade 1, then decrease dose level.

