6.5.1.4 Follow-up on amylase or lipase elevation (\geq CTCAE Grade 3)

Participants with amylase or lipase elevation \geq CTCAE Grade 3 must be tested weekly (or more frequently if clinically indicated) until \leq Grade 1 (or baseline). After resumption of dosing, continue to test weekly for one additional cycle. If no reoccurrence of \geq Grade 2 event, continue monitoring every cycle.

An exception to these follow-up guidelines will be made for cases of isolated amylase elevations in which amylase fractionation demonstrates that pancreatic amylase is \leq Grade 1. In such cases, total amylase and fractionated amylase should be monitored weekly (or more frequently if clinically indicated) for 4 weeks. If pancreatic amylase remains \leq Grade 1, subsequent monitoring must be performed at least every 4 weeks (or more frequently if clinically indicated).

Participants who discontinue trial treatment due to pancreatic toxicity must be monitored weekly (or more frequently if clinically indicated) until the event resolves to \leq Grade 1 or stabilization occurs (no CTCAE v4.03 grade change over 4 weeks).

If amylase and/or lipase elevations are accompanied by new or progressive unexplained abdominal symptoms such as severe pain or vomiting, withhold trial treatment, then perform diagnostic procedures (e.g., abdominal CT scan or ultrasound) to exclude pancreatic pathology.

See also dose modification guidelines described in [Table 6-3](#) “Criteria for dose reduction/interruption and re-initiation of alpelisib for adverse drug reactions”.

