8.4.3 Laboratory evaluations

Clinical laboratory analyses are to be performed on-site at Screening (Day -28 to Day -1), Cycle 1, Day 1, and at the EOT visit, and at a local laboratory during remote participation. SMBG will be performed by the participant. Novartis must be provided with a copy of all the laboratories' certification (if applicable), and a tabulation of the normal ranges and units of each parameter collected in the CRF. Any changes regarding normal ranges and units for laboratory values assessed during the trial must be reported via an updated tabulation indicating the date of revalidation.

The laboratory evaluation collection plan is presented in [Table 8-4](#). Visit windows of \pm 3 days are allowed for laboratory evaluations.

The investigator is responsible for reviewing all laboratory reports for participants in the trial and evaluating any abnormalities for clinical significance. Clinically significant abnormalities must be recorded as either medical history/current medical conditions or AEs as appropriate. At any time during the trial, abnormal laboratory parameters which are clinically relevant and require an action to be taken with trial treatment (e.g., require dose modification and/or interruption of trial treatment, lead to clinical symptoms or signs, or require therapeutic intervention), whether specifically requested in the protocol or not, will be recorded on the AE eCRF page. Laboratory data will be summarized using the CTCAE version 4.0.3.

Unscheduled assessments may be performed if medically indicated to assess a (potential) AE or when needed by the treating physician for decision making (e.g. dose modifications).

Table 8-4 Laboratory evaluation collection plan

Test Category	Test Name	Screening Day -14 to Day -1	Treatment phase	End of Trial Visit
Hematology	Hemoglobin, White blood cells, Differential (Leukocytes, Neutrophils, Thrombocytes), and Platelets.	Mandated	D1 of Cycle 2, and thereafter Day 1 of each cycle	Mandated
Chemistry	For all participants: C-Reactive Protein, Albumin, Alkaline Phosphatase, alanine aminotransferase, Aspartate aminotransferase, Bilirubin, Creatinine, Sodium, Potassium, Cancer Antigen 15-3, Lactate Dehydrogenase (LDH). For participants treated with SGLT2 inhibitors with or without metformin: ketones	Mandated	D1 of Cycle 2, and thereafter Day 1 of each cycle	Mandated

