	Fasting Plasma Glucose	Mandated	Day 1, and Day 15 of Cycle 1, Day 1 of Cycle 2, and thereafter Day 1 of each cycle Day 1 and Day 15 of Cycle 1, if accepted by local approved SmPC, FPG evaluation could be replaced by SMBG assessment, and this will not be considered protocol deviation.	Mandated.
	SMBG	-	Daily from Day 2 to Day 14 of Cycle 1, and thereafter as clinically indicated	
	Glycosylated hemoglobin (HbA1c)	Mandated	Day 1 of Cycle 2, Cycle 5, Cycle 8, and Cycle 11	Mandated
	Serum pregnancy test	Mandated	-	-

Note: All laboratory analyses will be performed locally.

SMBG=self-monitoring blood glucose

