13.4 Quality control and quality assurance

Novartis maintains a robust Quality Management System that includes all activities involved in quality assurance and quality control, to ensure compliance with written Standard Operating Procedures as well as applicable global/local GCP regulations and ICH Guidelines.

Audits of investigator sites, vendors, and Novartis systems are performed by auditors, independent from those involved in conducting, site monitoring or performing quality control of the clinical trial. The clinical audit process uses a knowledge/risk based approach.

Audits are conducted to assess GCP compliance with global and local regulatory requirements, protocols and internal standard operative procedures, and are performed according to written Novartis processes.

14 Protocol adherence

This protocol defines the trial objectives, the trial procedures and the data to be collected on trial participants. Additional assessments required to ensure safety of participants should be administered as deemed necessary on a case by case basis. Under no circumstances including incidental collection is an investigator allowed to collect additional data or conduct any additional procedures for any purpose involving any treatment under the protocol, other than the purpose of the trial. If despite this interdiction prohibition, data, information, observation would be incidentally collected, the investigator shall immediately disclose it to Novartis and not use it for any purpose other than the trial, except for the appropriate monitoring on trial participants.

Investigators ascertain they will apply due diligence to avoid protocol deviations. If an investigator feels a protocol deviation would improve the conduct of the trial this must be considered a protocol amendment, and unless such an amendment is agreed upon by Novartis and approved by the IEC and Health Authorities, where required, it cannot be implemented.

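### Table 6-3 orders an alpelisib hold for asymptomatic amylase or lipase above 2.0 × ULN, but none of the 11 scheduled on-treatment chemistry draws measures either enzyme

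*Protocol*

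**What the plan says.** **The rule.** Protocol Section 6.5, Table 6-3, has a row for amylase and/or lipase elevation without symptoms. Up to 2.0 × ULN the dose is maintained. Above that (Grade 3 or higher) the instruction is "Omit dose until resolved to baseline, then" to restart at the same level if resolution took 14 days or less, and at a lower level otherwise. Dosing may continue through an isolated amylase rise if fractionation shows pancreatic amylase at Grade 1 or lower.

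**The schedule.** Section 8.4.3, Table 8-4, sets out the chemistry panel: "For all participants: C-Reactive Protein, Albumin, Alkaline Phosphatase, alanine aminotransferase, Aspartate aminotransferase, Bilirubin, Creatinine, Sodium, Potassium, Cancer Antigen 15-3, Lactate Dehydrogenase (LDH". That is 11 analytes, with ketones added for participants on SGLT2 inhibitors. The panel is due at screening, on Day 1 of Cycle 2 and of every later cycle, and at end of trial. Table 8-1 shows a full chemistry profile without naming its contents and has no row for either enzyme.

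**Other places that mention the enzymes.** Inclusion criterion 8 (Section 5.1) caps fasting amylase at 2 × ULN and "Fasting Serum lipase" at ULN. Section 6.5.1.4 requires weekly testing for participants who already have a Grade 3 or higher value. If there is no recurrence after restart, it tells the investigator to carry on with per-cycle monitoring.

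**Discretionary testing.** Section 8.4.3 states: "Unscheduled assessments may be performed if medically indicated to assess a (potential) AE or when needed by the treating physician for decision making". Section 14 adds: "Additional assessments required to ensure safety of participants should be administered as deemed necessary on a case by case basis".

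**The concern.** A mandatory hold for a laboratory value without symptoms works only if someone measures that value. By definition this row concerns participants who give no clinical cue, and most of them are at home under remote follow-up. If no planned draw contains the enzyme, a participant above the protocol's own threshold can stay on full-dose alpelisib, with detection depending on whether a test happened to be ordered.

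The wording of Section 6.5.1.4 suggests an oversight more than a decision. Telling the investigator to carry on monitoring each cycle presupposes a per-cycle test, and the schedule contains none. Elsewhere the protocol takes pancreatic toxicity seriously: both enzymes are capped at entry, recent acute or any chronic pancreatitis is an exclusion, and only one dose reduction is allowed for pancreatitis.

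**Working it through.** The documents state no figure to reproduce. The check is a count of scheduled tests against each laboratory-value row of Table 6-3, for a participant who completes all cycles.

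**Inputs**
- Planned treatment: 12 cycles of 28 days (Section 6.1.3), so 12 × 28 = 336 days.
- On-treatment chemistry: Day 1 of Cycle 2 and of each later cycle (Table 8-4).
- Fasting plasma glucose: "Day 1, and Day 15 of Cycle 1, Day 1 of Cycle 2, and thereafter Day 1 of each cycle" (Table 8-4). Self-monitored glucose may replace the two Cycle 1 values.
- Panel contents: the 11 analytes of Table 8-4, plus ketones for some participants.

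**On-treatment draws.** Day 1 of Cycles 2 to 12 gives 12 − 2 + 1 = 11. The count rests on the wording of Table 8-4, because the columns of Table 8-1 may have shifted in text extraction.

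**Draws that could trigger each row, after the first dose and before end of trial**

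| Table 6-3 row | Analyte in Table 8-4? | Scheduled tests |
|---|---|---|
| Fasting glucose | yes | 1 (Cycle 1 Day 15) + 11 = 12 |
| Isolated total bilirubin | yes | 11 |
| "Isolated AST or ALT elevation" | yes | 11 |
| Combined ALT/AST and total bilirubin | yes, all from the same draw | 11 |
| Asymptomatic amylase and/or lipase | no | 0 of 11 |

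**Other routes to a value**
1. Criterion 8 yields one pre-dose value of each enzyme. It cannot detect a rise on treatment.
2. Section 6.5.1.4 begins after a Grade 3 or higher value is known, so it cannot supply the first such value.
3. Unscheduled testing under Section 8.4.3 or Section 14 needs a medical indication or a case-by-case judgement.
4. The instructions to withhold treatment and investigate new unexplained abdominal symptoms (note in Table 6-3, and Section 6.5.1.4) concern symptomatic participants, which this row does not.

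Only route 3 can reach the asymptomatic row, and it is discretionary.

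**After the change.** Both enzymes would be measured at 11 of 11 draws. Added on-treatment assays: 2 × 11 = 22 per completer. If all 20 planned participants completed 12 cycles, the ceiling would be 22 × 20 = 440.

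**The case against.** The best reply is that a dose-modification table says what to do if a value is found and does not promise to look for it. Alpelisib is marketed, participants are managed according to clinical practice (Section 4.5.1), and the events of special interest are hyperglycemia, rash and diarrhea. Symptomatic pancreatic trouble has its own instructions, and unscheduled tests are allowed. Routine enzyme testing would also cause some holds for isolated rises of doubtful importance. Much of this stands: it limits the severity, and without an incidence figure nobody can say how many rises would be missed. It does not remove the mismatch, because this row is written for participants without symptoms and Section 6.5.1.4 itself assumes per-cycle monitoring.

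A reader might be tempted to go further in several ways that the documents do not support.

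- **A testing gap during a hold.** Weekly testing in Section 6.5.1.4 may end at Grade 1 or baseline, while restart needs baseline. One might infer that lipase between 1.0 and 1.5 × ULN goes unmeasured and that the 14-day dose decision is left to chance. But the text runs "Grade 1 (or baseline). After resumption of dosing, continue to test weekly for one additional cycle", and continuing presupposes that weekly testing is still under way at restart. Section 6.5.1 also requires follow-up of interrupted participants to resolution or stabilization (or up to the end-of-trial visit), although without a weekly interval, and restart itself needs a baseline value.
- **Counting the end-of-trial draw.** No trial alpelisib remains to be held by then, so that draw does not belong in the count.
- **Reading the screening omission as specific to these enzymes.** Calcium, magnesium and INR are also required by criterion 8 and are also missing from Table 8-4.
- **A serious reporting distortion.** SAP Section 2.6.3 lists all laboratory data as well as Grade 3 or 4 abnormalities, so a lack of enzyme values would be visible.

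**Conclusion.** The point holds as a minor inconsistency between a safety rule and the assessment schedule. Table 6-3 mandates a hold for asymptomatic amylase and/or lipase above 2.0 × ULN, subject to the isolated-amylase exemption, and 0 of 11 scheduled on-treatment chemistry draws can reveal it. The four other laboratory-value rows each have a test every cycle.

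This rests on two assumptions: that Table 8-4 is the definition of the full chemistry profile named in Table 8-1, and that the participant completes 12 cycles (fewer draws otherwise, still with none including the enzymes). It does not show that any participant was harmed or that any rise was missed. The study stopped early for low enrollment and its data will only be listed (SAP Section 1), so the practical value lies in any reuse of this design and in one clarifying statement in the report.

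**What to change.** For any reuse of the protocol, add amylase and lipase to the Table 8-4 chemistry row at screening and on Day 1 of each cycle from Cycle 2. The screening entry adds no new requirement, since criterion 8 already needs both values, and it records the baseline to which a hold must resolve. The on-treatment entries make the Table 6-3 rule operable and give the per-cycle monitoring in Section 6.5.1.4 something to continue.

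The cost is the 22 on-treatment assays per completer worked out above, on blood already being drawn, and one edited table row. The clinical downside is some holds for isolated enzyme rises, which the pancreatic-amylase exemption limits for amylase but not for lipase.

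For the stopped study, add one sentence to the clinical study report saying that these enzymes were not scheduled on treatment, so that their absence from the Grade 3 or 4 laboratory listing is not read as absence of events.

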6.5.1 Follow-up for toxicities

Participants, whose treatment is interrupted or permanently discontinued due to an AE or a clinically significant laboratory value, must be followed until resolution or stabilization of the event (and/or up to EOT visit), whichever comes first. Further guidelines and recommendations for the management of specific trial treatment combination-induced toxicities are provided below.

6.5.1.1 Management of pneumonitis/interstitial lung disease

Alpelisib is associated with pneumonitis/interstitial lung disease. Closely monitor all participants for signs and symptoms of pneumonitis.

All participants will be routinely asked about and observed for the occurrence of AEs including new or changed pulmonary symptoms (consistent with lung abnormalities).

Participants who are suspected to have developed pneumonitis should interrupt (alpelisib and combination drug) immediately and undergo appropriate imaging (high resolution CT scan) and broncho-alveolar lavage; biopsy should be considered if clinically appropriate. Infectious causes of interstitial lung disease should be ruled out. Investigators should follow institutional practice for management of pneumonitis which generally includes treatment with high dose corticosteroids; antibiotic therapy should be administered concurrently if infectious causes are suspected. Consultation with a pulmonologist is highly recommended for any pneumonitis case during the trial treatment.

After ruling out infectious etiology and upon making a diagnosis of pneumonitis, permanently discontinue treatment with alpelisib and promptly initiate appropriate treatment and supportive measures.

6.5.1.2 Guidelines for the treatment of trial drug-induced skin toxicity

Skin toxicity is a class-effect AE observed with PI3K inhibitors agents.

Close monitoring of potential skin reactions will be performed and will be reported as AE (see [Section 4.5.3 “Risk Management Strategies”](#)). The most frequent skin AEs reported are: maculopapular rash (only a minority present acneiform rash); pruritus and dry skin. The onset is typically within the first 2 months of treatment start and is reversible with adequate co-medication and treatment interruption if needed. Skin reactions may improve over several weeks. Consultation with a dermatologist is highly recommended for better assessment and management of alpelisib-induced skin toxicity at any grade, and mandated if severe cutaneous reaction like Stevens-Johnson Syndrome, Toxic Epidermal Necrolysis, Erythema Multiforme or Drug Reaction with Eosinophilia and Systemic Symptoms (DRESS) is suspected.

Workup for skin toxicity events may include a complete blood count with differential, and a full chemistry panel.

Antihistamines administered prior to rash onset may decrease incidence and severity of rash based on Study CBYL719C2301; therefore, at the investigator’s discretion, non-sedating antihistamines (e.g. cetirizine (Zyrtec®), fexofenadine (Allegra®), loratadine (Claritin®)) may be used as prophylactic treatment starting at Cycle 1, Day 1 to reduce severity of rash in all participants and especially for participants with a history of atopy such as allergic rhinitis, asthma, atopic dermatitis, or drug allergies.

Recommended therapies for skin toxicity events of all grades and as clinically indicated include:

- Mid to high potency topical steroids: triamcinolone 0.01% or fluocinonide 0.05% twice daily for at least 28 days. Recommend spray, lotion, or cream preparation for ease of application on trunk. For scalp involvement, recommend a foam or solution preparation.

- Gamma-aminobutyric acid agonists: gabapentin 300 mg every 8 hours, pregabalin 50 to 75 mg every 8 hours (to adjust of renal impairment). Depending on participant's clinical condition, be aware of potential and common side effects observed with gamma-aminobutyric acid agonists such as: somnolence, dizziness (both drugs) and peripheral edema (gabapentin) among others AEs.

For grade 4 skin events or any grade of severe cutaneous reactions (including Stevens-Johnson syndrome, Toxic epidermal necrolysis, Erythema multiforme, DRESS), alpelisib treatment must be permanently discontinued without any re-challenge.

If dry skin is reported, it is recommended that participants with dry skin use mild and fragrance-free soaps and detergents.

Although preclinical experiments demonstrated that alpelisib have no potential phototoxic effect, participants should avoid sun exposure during treatment with alpelisib, especially when they already have experienced rash or other skin toxicities as the increased blood flow of the skin may worsen skin symptoms. Participants should be advised to take measures to protect themselves from direct exposure to sunlight, including the wearing of sunglasses as well as the regular use of sunscreen, hats, long-sleeve shirts, and long pants when outdoors.

